**Overall Design:**

This is a multicentre, randomized, double-blind, placebo controlled, parallel group, phase 3 Long Term Extension (LTE) study designed to evaluate the safety, and tolerability of 210 mg Q4W (SC) of tezepelumab in adults and adolescents with severe, uncontrolled asthma on medium to high-dose ICS and at least one additional asthma controller with or without OCS. Subjects who have continued to receive investigational product and have attended the End of Treatment (EOT) visit in one of the predecessor studies, week 52 in study D5180C00007 or week 48 in study D5180C00009, on investigational product may be eligible to enroll into this study if they fulfil the inclusion/exclusion criteria. Those who prematurely discontinue IP during the predecessor studies will not be eligible for the LTE study.

CCI

The study will consist of a screening/randomization visit at the timepoint of the EOT Visit in the predecessor study for all subjects. A treatment period will follow whereby all subjects will continue on investigational product for an additional year, up to a total of 104 weeks (including predecessor study treatment period), followed by a post-treatment follow-up period of 12 weeks. Subjects who prematurely discontinue investigational product (IP) during the LTE study will be encouraged to undergo appropriate study visits/procedures for the full treatment period. CCI

[figure not shown]
Tezepelumab - D5180C00018

**Study Period:**Estimated date of first subject enrolled *Q1 2019*Estimated date of last subject completed *Q2 2022***Number of Subjects**

Subjects who have continued to receive IP and attended the EOT visit in one of the predecessor studies may be eligible to enroll in the study. It is anticipated that approximately 975 subjects will enroll worldwide. This assumes that 90% of subjects in the predecessor studies complete dosing, and that 90% of those continue into the Long-Term Extension Study (i.e. approximately 860 subjects transitioning from D5180C00007 and approximately 115 subjects transitioning from D5180C00009).

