## 4 Study Design

### 4.1 Overall design

For an overview of the study design see [Figure 1](#), in Section [1.3](#). For details on treatments given during the study, see Section [6.1](#) Treatments Administered.

For details on what is included in the safety and efficacy endpoints, see Section [3](#) Objectives and Endpoints.

This is a multicentre, randomized, double-blind, placebo-controlled, parallel group, long-term extension study to evaluate the safety and tolerability of 210 mg Q4W SC of tezepelumab in adults and adolescents with severe uncontrolled asthma. Subjects who have continued to receive investigational product and have attended the EOT visit in one of the predecessor studies may be eligible to enroll into this study if they fulfil the inclusion/exclusion criteria.

Tezepelumab - D5180C00018

This study will be run at approximately 350 sites worldwide and will randomize approximately 975 subjects worldwide. All subjects will be re-randomized in this study to maintain the blinding. Subjects previously randomized to the 210 mg tezepelumab Q4W SC arm in either of the predecessor studies, will be assigned and remain on 210 mg tezepelumab Q4W SC dosing in the LTE study. Subjects randomized to placebo arm in the predecessor studies will be re-randomized in a 1:1 ratio to either 210 mg tezepelumab or placebo, both administered Q4W SC. Given the randomization scheme of subjects in the predecessor studies, this will give an overall subject distribution of 3:1 (tezepelumab:placebo).

Subjects who prematurely discontinue IP or do not attend the EOT visit in one of the predecessor studies will not be eligible to participate in the Long-Term Extension (LTE) study.

In order to provide sufficient time for subjects to consider participation in this study, and to ensure an uninterrupted dosing regimen, as subjects transition between the predecessor study and this study, subjects will be provided with the ICF at/after the visit at which they receive their last dose of IP in the predecessor study and will be asked to sign the ICF at Visit 1 of this study prior to any study-specific procedures being performed.

Section 6.5 (Table 6 and Table 7) provides a list of medication restrictions and prohibitions to be followed throughout conduct of the clinical trial. See inclusion criteria Section 5.1.

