## 5.2 Exclusion criteria

### Medical conditions

1. Any clinically important pulmonary disease other than asthma (e.g., active lung infection, Chronic Obstructive Pulmonary Disease (COPD), bronchiectasis, pulmonary fibrosis, cystic fibrosis, hypoventilation syndrome associated with obesity, lung cancer, alpha 1 anti-trypsin deficiency, and primary ciliary dyskinesia) or pulmonary or systemic diseases, other than asthma, that are associated with elevated peripheral eosinophil counts (e.g., allergic bronchopulmonary aspergillosis/mycosis, Churg-Strauss syndrome, hypereosinophilic syndrome).
2. Any disorder, including, but not limited to, cardiovascular, gastrointestinal, hepatic, renal, neurological, musculoskeletal, infectious, endocrine, metabolic, hematological, psychiatric, or major physical impairment that is not stable in the opinion of the Investigator and could:
  - Affect the safety of the subject throughout the study
  - Influence the findings of the study or the interpretation
  - Impede the subject's ability to complete the entire duration of study

Tezepelumab - D5180C00018

3. History of chronic alcohol or drug abuse within 12 months prior to Visit 1
4. Current malignancy or malignancy that developed during a predecessor study (subjects who had a basal cell carcinoma or a localized squamous cell carcinoma of the skin which was resected for cure will not be excluded)
5. Exclusion criterion #5 removed with version 2.0 of the clinical study protocol
6. Major surgery or planned surgical procedures requiring general anaesthesia or inpatient status for > 1 day during the conduct of the study, unless approved by the sponsor Study Physician

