### 9.3 Populations for analyses

For purposes of analysis, the following populations are defined:

Population	Description
Safety analysis set	
All subjects who were randomized and received at least 1 dose of investigational product in any of the predecessor studies, irrespective of their protocol adherence and continued participation in any of the studies, and regardless of their enrolment into the LTE study.
 
Subjects will be assigned according to their randomized treatment. However, if a subject randomised to placebo receives an incorrect treatment, all data after the date the incorrect treatment was received within that time period (predecessor study, LTE study) will be excluded from the analysis, and listed separately

Full analysis set	
All subjects who were randomized and received at least 1 dose of investigational product in any of the predecessor studies, irrespective of their protocol adherence and continued participation in any of the studies, and regardless of their enrolment into the LTE study.
 
Subjects will be assigned according to their randomized treatment

In addition, to the populations defined above, a subset (safety analysis set-long term extension: “SAF-LTE”, full analysis set-long term extension: “FAS-LTE”) of each population will be defined which includes only subjects who enrolled and received at least 1 dose of IP in the LTE study. As these are based on subjects who complete the predecessor study, it may be subject to selection bias especially for measures of asthma control, where less severe subjects may be more likely to complete the predecessor study and enroll into the LTE study; these populations will be

Tezepelumab - D5180C00018

[figure not shown]
used for supportive analyses only. The number of subjects discontinuing IP and patterns of discontinuations will be considered when interpreting the data.

CCI [REDACTED]

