2 ANALYSIS SETS

2.1 Definition of analysis sets

For purposes of analysis, the following populations are defined below in Table 2.

Note that subjects included in the SAF and SAF-LTE analysis sets will be assigned to the treatment they are randomised to in the predecessor and LTE studies. In the case of discrepancies between the randomised and actual treatment, where a subject randomised to placebo, receives at least one dose of tezepelumab then all data from the date of the incorrect treatment within that time period (predecessor study, LTE study) will be excluded from the analysis and will be listed separately.

This is a different approach from the reporting of the individual predecessor studies, where treatment is based on the treatment subjects received in the case of any discrepancies between randomised and actual treatment. The reason for the difference in approaches is to avoid adding further complexity to the treatment groups as defined in Section 2.1.2.

Table 2 Analysis sets

| Population | Description |
|---------------------------|--|
| Safety analysis set (SAF) | All subjects who were randomised and received at least 1 dose of IP in any of the predecessor studies, irrespective of their protocol adherence and continued participation in any of the studies, and regardless of their enrolment into this LTE study. Subjects will be assigned according to their randomised treatment. However, if a subject randomised to placebo receives an incorrect treatment, all data after the date the incorrect treatment was received within that time period (predecessor study, LTE study) will be excluded from the analysis, and listed separately. If a subject randomised to tezepelumab receives an incorrect treatment, it will still be regarded as a tezepelumab subject and no data will be excluded after the dose of placebo. Other incorrect dosing, if any, will be handled case-by-case. |

| Population | Description |
|-------------------------|---|
| SAF-LTE | Subjects who were randomised and received at least 1 dose of IP in the LTE study. |

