2.1.2 Treatment groups

There are 5 possible groupings across the predecessor and LTE studies as shown in Figure 2 below.

Figure 2 Treatment groupings

[figure not shown]

Note: Groups 2 and 5 reflect subjects in the predecessor studies who do not enrol in the LTE study.

The following treatment groups for analyses will be considered, where time from first dose is applicable for the safety analysis, and time from randomisation is applicable for the efficacy analysis:

Primary (based on the SAF and FAS analysis sets):

[figure not shown]
- Randomised Tezepelumab (Rand Teze): All subjects originally randomised to tezepelumab in the predecessor studies. Will include all data from first dose/randomisation in the predecessor studies to end of the LTE study. (A, B and C)
- Randomised Placebo (Rand Pbo): All subjects originally randomised to placebo in the predecessor studies. Will include all data from first dose/randomisation in predecessor studies up until switch to tezepelumab, and all data from first dose/randomisation in the predecessor studies to end of the LTE study for subjects randomised to placebo in the predecessor studies and the LTE study. (D, F, G and H)

Supportive (based on the SAF-LTE and FAS-LTE analysis sets):

[figure not shown]
- Tezepelumab Predecessor+Tezepelumab LTE (Teze+Teze): All subjects originally randomised to tezepelumab in the predecessor studies and re-randomised to tezepelumab in the LTE study. Will include all data from first dose/randomisation in the predecessor study to end of the LTE study for only subjects enrolled into the LTE study. (A and B)
- Placebo Predecessor+Placebo LTE (Pbo+Pbo): All subjects randomised to placebo in the predecessor studies, and later re-randomised to placebo in the LTE study. Will

include all data from first dose in predecessor studies until end of the LTE study for only subjects enrolled into the LTE study. (F and G)

[figure not shown]
Supportive (for exposure summaries and rare events based on the SAF analysis set):

[figure not shown]
• All Tezepelumab (All Teze): All subjects randomised to tezepelumab in the predecessor studies and subjects randomised to tezepelumab in the LTE study. It will include all data from time of first dose/randomisation to tezepelumab. (A, B, C and E)

Additional (for the assessment of durability of benefit based on the SAF-LTE and FAS-LTE analysis sets):

- Tezepelumab Predecessor+Tezepelumab LTE (Teze+Teze): as defined above

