4.5 Safety and tolerability

4.5.1 Adverse events

AEs will be summarised separately for the on-treatment and on-study periods as defined in Section 3.2.2 unless stated otherwise. All AE summaries will be presented by analysis set and treatment groups as follows:

- SAF (Randomised Tezepelumab and Randomised Placebo), overall only
- SAF-LTE (Tezepelumab Predecessor+Tezepelumab LTE and Placebo Predecessor+Placebo LTE), overall and by time period
- SAF-LTE (Placebo Predecessor+Tezepelumab LTE), predecessor and LTE periods

All AEs will be listed for the SAF-LTE analysis set. AEs occurring during the screening/runin period or occurring post-treatment will be highlighted with an asterisk in the listing, but
not summarised separately. In addition, for subjects with a delay between the predecessor
study EOT visit and LTE study Visit 1, a listing of AEs starting more than 33 days after the
last dose of IP in the predecessor study but prior to Visit 1 in the LTE study will be provided.
A further listing of AEs occurring between the LTE study Visit 1 and the date of first dose in
the LTE study will be provided for those subjects who do not receive their first dose of IP in
the LTE study at Visit 1 of the LTE study. Information related to the outcome of any
pregnancies will also be listed for the SAF-LTE analysis set.

For each of the summaries below, the following will be included:

- Number and percentage of subjects reporting at least one AE.
- Exposure adjusted incidence rates (as defined in Section 3.2.2) per 100 subject-years

An overall summary table will be produced showing the following categories: any AEs, serious adverse events (SAEs), AEs with a fatal outcome, and AEs leading to discontinuation of IP (DAEs).

All AEs will be summarised by system organ class (SOC) and preferred term (PT) assigned to the event using the MedDRA dictionary. For each PT, for the number of subjects reporting at least one occurrence of the event, subjects with multiple occurrences of the same PT will only be counted once for the calculation of incidence rates.

Similar summaries by SOC and PT will also be presented for:

- SAEs
- Fatal AEs
- DAEs on-treatment period only

- DAEs causally related to IP on-treatment period only
- SAEs leading to discontinuation of IP on-treatment period only
- Each AESI category separately on-treatment period only

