| C00009 | OCS baseline to optimised dose | ✓ | | ✓ | | | |
| Both | Disallowed Medications (prior) | ✓ | | ✓ | | √Overall | |
| Both | Disallowed Medications (on-treatment) | ✓ | | ✓ | √ | √ | |
| Both | Disallowed Medications (post-treatment) | ✓ | | ✓ | | √Overall | |
| Both | Biologics (prior) | ✓ | | ✓ | | √Overall | |
| Both | Biologics (post-treatment) | √ | | ✓ | | ✓ Overall | |
| Exposur | re and compliance (Section 4.4) | | | | | | |

| Analysis | Analysis sets | | //FAS | SAF-LTE/FAS-LTE | | | CCI |
|-------------------------|---|--------------------------|-------------|-----------------|--------------------------|-----------------------|-----|
| Treatme | nt groups | (Rand Teze/ Rand Pbo) | (All Teze) | ` | ze+Teze/ o+Pbo) | (Pbo+Teze) | |
| Study | Data | Overall | Overall | Overall | By period (PreD, LTE) | By period (PreD, LTE) | |
| Both | Exposure | ✓ | √ +C | ✓ | ✓ | ✓ | |
| Both | Compliance | ✓ | | ✓ | ✓ | ✓ | |
| Both | Total number of dosing occasions | ✓ | ✓ | ✓ | | | |
| SAFETY and TOLERABILITY | | | | | | | |
| Adverse | events (Section 4.5.1, 4.7.2) | | | T | | | |
| Both | Overall summary | √+SG | √On-Trt | √ | ✓ | ✓ | |
| Both | AEs by SOC/PT | √+SG | √On-Trt | ✓ | √ | ✓ | |
| Both | AEs by PT and causality | ✓ | | ✓ | ✓ | ✓ | |
| Both | AEs by PT and max intensity | ✓ | | ✓ | ✓ | ✓ | |
| Both | SAEs by SOC/PT | √+SG | √On-Trt | √+SG | √+SG | ✓ | |
| Both | Fatal AEs by SOC/PT | ✓ | | ✓ | ✓ | ✓ | |
| Both | DAEs by SOC/PT | √+SG | √On-Trt | √+SG | √+SG | ✓ | |
| Both | DAEs causally related to IP by SOC/PT | ✓ | | ✓ | ✓ | ✓ | |
| Both | SAEs leading to discontinuation by SOC/PT | ✓ | | ✓ | ✓ | ✓ | |
| Both | Each AESI category by SOC/PT | ✓ | √On-Trt | √ | √ | √ | |
| Both | Each AESI category by PT and causality | ✓ | | ✓ | ✓ | ✓ | |

| Analysis sets | | SAF | SAF/FAS | | SAF-LTE/FAS-I | LTE | CCI |
|--|---|--------------------------|------------|----------|--------------------------|--------------------------|-----|
| Treatme | nt groups | (Rand Teze/ Rand Pbo) | (All Teze) | , | ze+Teze/ o+Pbo) | (Pbo+Teze) | |
| Study | Data | Overall | Overall | Overall | By period (PreD, LTE) | By period (PreD, LTE) | |
| Both | Further summaries of AESI of injection site reactions | ✓ | | √ | ✓ | √ | |
| Both | Most common AEs by PT only | ✓ | | ✓ | ✓ | ✓ | |
| Both | Adjudicated AEs | ✓ | | ✓ | ✓ | ✓ | |
| Both | AESIs - exposure adjusted occurrence rate | ✓ | √On-Trt | ✓ | ✓ | √ | |

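### SAF-LTE rates of fatal AEs and AE-related discontinuations include a predecessor year that entry rules leave almost empty: overall rates are about half the LTE-period rate, and period comparisons mislead

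*SAP*

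**What the plan says.** **Who is in the set.** SAP 2.1 defines SAF-LTE as "Subjects who were randomised and received at least 1 dose of IP in the LTE study".

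**When its exposure starts.** For Teze+Teze, SAP 2.1.2 states: "Will include all data from first dose/randomisation in the predecessor study to end of the LTE study". The Pbo+Pbo and Pbo+Teze groups also start at the first predecessor dose. SAP 3.2.2 defines the rate as subjects with an event divided by total exposure, and assigns AEs to periods by onset date. SAP 3.1.1 merges AEs that are ongoing across the two studies into one record where possible.

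**Who may enter.** Protocol 4.1, on LTE entry: "Subjects who prematurely discontinue IP or do not attend the EOT visit in one of the predecessor studies will not be eligible to participate". The synopsis repeats this: "Those who prematurely discontinue IP during the predecessor studies will not be eligible for the LTE study". Inclusion criterion 5 also requires that IP discontinuation criteria have not been met. Exclusion criterion 4 in Protocol 5.2 is "Current malignancy or malignancy that developed during a predecessor study", with an exception for basal cell or localized squamous cell skin carcinoma resected for cure.

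**What is tabulated.** SAP 4.5.1 plans rates for "SAF-LTE (Tezepelumab Predecessor+Tezepelumab LTE and Placebo Predecessor+Placebo LTE), overall and by time period", and for Pbo+Teze by period only. In SAP Table 10 the row "Fatal AEs by SOC/PT" is ticked for all of these columns. So are the rows for DAEs (all and causally related), SAEs leading to discontinuation, each AESI category and adjudicated AEs. For the SAF, SAP 4.5.1 gives no period split.

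**What the protocol promised.** Protocol 9.4.2 plans summaries overall and by time period for four groups, including both SAF groups. SAP Section 6 lists only one change from the protocol, the added LTE analysis set.

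**Existing caveat.** Protocol 9.3 says of the LTE subsets that "it may be subject to selection bias especially for measures of asthma control". Both documents call these sets supportive.

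**The concern.** Membership of SAF-LTE is decided at about Week 52 or 48, but person-time is counted from Week 0. For outcomes that bar entry, the time before entry is guaranteed time: it adds to the denominator and almost nothing to the numerator.

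Three displays are affected:

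- The overall SAF-LTE rate is diluted.
- The by-period table shows a near-empty first year followed by a positive second year. This can be read as a risk that emerges late.
- The Pbo+Teze table sets a placebo year in which these events could hardly appear against a tezepelumab year in which they can. This can be read as harm from starting tezepelumab.

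Long-term safety is the primary objective, so AE rates over time will be examined closely. As the SAP stands, the only AE tables split by predecessor and LTE period are in the selected set.

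**Working it through.** **1. The plan's own durations.** Protocol 4.1 gives 52 LTE weeks after D5180C00007 (52 weeks) and 56 after D5180C00009 (48 weeks): 52 + 52 = 104 and 48 + 56 = 104. The expected numbers also add up: 860 + 115 = 975. There is no alpha, power or event target to reproduce.

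**2. Formula.** With no countable predecessor events, the rate definition in SAP 3.2.2 gives

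overall rate / LTE-period rate = LTE exposure / (predecessor + LTE exposure).

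**3. Full follow-up.** Predecessor time is 364 days (D5180C00007) or 336 days (D5180C00009). The on-treatment period ends 33 days after the Week 100 dose, at 700 + 33 = 733 days. The on-study period for a subject followed to Week 116 ends at 812 days.

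| Window | D5180C00007 | D5180C00009 |
|---|---|---|
| Planned 104 weeks | 364/728 = 0.500 | 392/728 = 0.538 |
| On-treatment | 369/733 = 0.503 | 397/733 = 0.542 |
| On-study to Week 116 | 448/812 = 0.552 | 476/812 = 0.586 |

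SAP 4.5.1 uses the last two windows. DAEs and SAEs leading to discontinuation are summarised on-treatment only; fatal AEs are summarised in both windows.

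**4. LTE dropout.** The planned rates are redacted, so annual dropout d of 5% to 20% is assumed, with exponential loss. Mean LTE time is (1 − exp(−λL))/λ, where λ = −ln(1 − d)/52 and L is the LTE length in weeks. The on-treatment factor becomes 0.497 to 0.476 (D5180C00007) and 0.535 to 0.512 (D5180C00009). The on-study factor becomes 0.544 to 0.518 and 0.578 to 0.551.

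**5. Illustration (assumed rates).** Take 430 Teze+Teze subjects from D5180C00007 (half of 860), one year in each period, and a true rate of 1 per 100 subject-years. Then 4.3 subjects have an event in the LTE. The table shows 0 for the predecessor period, 4.3/430 = 1.0 for the LTE and 4.3/860 = 0.5 overall. At true rates of 0.5 and 2 per 100 subject-years the overall figures are 0.25 and 1.0.

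**6. Between arms.** With LTE-period rates of 2 and 1 per 100 subject-years, the ratio is 2.0 and the difference 1.0. Overall the rates become 1.0 and 0.5: the ratio stays 2.0 and the difference falls to 0.5. This assumes equal follow-up. If one arm had 5% dropout and the other 20%, the ratio would shift by only 0.497/0.476 = 1.04.

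**7. Malignancy.** Let s be the share of the malignancy rate due to exempt skin carcinoma, which can occur in either period. The planned-window factor is 0.5(1 + s) for D5180C00007 and (336/728)s + 392/728 for D5180C00009.

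| s | D5180C00007 | D5180C00009 |
|---|---|---|
| 0 | 0.500 | 0.538 |
| 0.25 | 0.625 | 0.654 |
| 0.5 | 0.750 | 0.769 |
| 1 | 1.000 | 1.000 |

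**The case against.** The strongest reply is that these tables are supportive, no hypothesis is tested, and the primary objective is answered on the SAF by originally randomised group. The SAF keeps predecessor deaths, discontinuations and malignancies. The undiluted LTE-period rate stands beside the diluted one, and a parallel Pbo+Pbo column would show the same near-zero-then-positive pattern. Protocol 9.3 also warns of selection in general terms and says that patterns of discontinuation will be considered in interpretation. All of this stands, and it limits the severity.

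It does not remove the point. A preserved between-arm ratio does not help a within-group reading over time, and Pbo+Teze has no parallel arm that makes the same switch. The caveat does not tell a reader that particular cells are near zero because of eligibility.

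A reader might go further in three ways that the documents do not support:

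- **That these events are impossible in the predecessor year.** An AE that began there and later proved fatal or led to stopping IP in the LTE is assigned by onset date, so the cells are near zero, not necessarily zero.
- **That malignancy is halved like deaths.** Exempt skin carcinomas do not bar entry, and the SMQ-based definition in SAP 8.1.4 states no exception for them.
- **That all adjudicated events are affected.** These include MACE, and no entry criterion excludes a subject for a past non-fatal MACE as such.

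**Conclusion.** The point holds for fatal AEs, DAEs (all and causally related) and SAEs leading to discontinuation in SAF-LTE. The overall rate for Teze+Teze and Pbo+Pbo is about 0.50 (on-treatment) to 0.55 (on-study) of the LTE-period rate for D5180C00007, and 0.54 to 0.59 for D5180C00009. LTE dropout lowers this somewhat. These factors assume negligible predecessor-onset events. For malignancy the factor runs from about 0.5 to 1.0 with the share of exempt skin cancers, which the documents do not give.

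Rate differences shrink by the same factors. Year-1 versus year-2 comparisons are misleading for these outcomes, as is the Pbo+Teze period comparison. A reader might infer that the primary safety result or the tezepelumab-to-placebo rate ratio is biased by this. Neither is: the SAF overall analysis does not condition on LTE entry, and both SAF-LTE arms are diluted alike when follow-up is similar.

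The missing SAF period split makes matters worse. It departs from Protocol 9.4.2 and is not declared in SAP Section 6. Severity is moderate and confined to supportive tables.

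**What to change.** In SAP 4.5.1 and Table 10:

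1. Restore the by-period AE summaries for the SAF (Randomised Tezepelumab and Randomised Placebo) that Protocol 9.4.2 promises. Take predecessor-year and 104-week rates of these outcomes from the SAF.
2. For SAF-LTE groups, including Pbo+Teze, give exposure-adjusted rates of fatal AEs, DAEs (all and causally related) and SAEs leading to discontinuation for the LTE period only, with LTE person-time. Drop the overall rate. Keep any predecessor-onset events visible as counts, with a footnote that the entry criteria exclude these outcomes.
3. For malignancy (AESI and adjudicated), keep every observed event and footnote the predecessor and overall columns. Give rates excluding exempt skin carcinoma for the LTE period only. Blanking the malignancy cells instead would hide events that really occurred.
4. Leave MACE as planned.

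The cost is SAP wording, edits to Table 10 and a few additional SAF by-period columns. No new data are needed.
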